The primary efficacy hypothesis is that TAVI with the TriGUARD 3 system is superior to standard (unprotected) TAVI for the primary hierarchical composite efficacy endpoint of all-cause mortality or any stroke at 30 days (Tier 1), NIHSS worsening 2-5 days post-procedure (Tier 2), freedom from any cerebral ischemic lesions detected by diffusion-weighted magnetic resonance imaging (DW-MRI) 2 to 5 days post-procedure (Tier 3), and total volume of post-procedure cerebral ischemic lesions detected by DW-MRI (Tier 4). In tier 1 death/stroke will be analyzed as time to event by days.

Each subject in the intervention group of phase II will be compared with every control subject (from phases I and II) based on the pre-specified hierarchy of adverse outcomes according to the Finkelstein-Schoenfeld method.² For example, if Subject A dies or has stroke and Subject B survives free of stroke to 30 days, Subject B wins (score +1) and Subject A loses (score -1). If both subjects die or have a stroke on the same day, it is equilibrium (score 0, otherwise the patient with the later (by at least a day) death/stroke will be the winner. If both patients had a stroke on the same day the comparison will move to the next tier of the hierarchy.

If neither subject experiences a Tier 1 event, the comparison moves to the next tier of the hierarchy. After all between-subject comparisons have been performed, scores are summed to obtain a cumulative score for each subject, and outcomes between treatment groups are then compared by the chi-square test.

Based on published clinical data from randomized controlled trials of subjects undergoing TAVI⁴⁻⁷ as well as data from the DEFLECT III randomized trial of TriGuard HDH vs. unprotected TAVI⁸ and the recent SENTINEL⁹ trial we assume the following hierarchical event rates:

Assumed Event Rates Phase II

	Assumed Control Rates	Assumed TriGUARD 3 Rates
Death or Stroke	11%	6%
Worsening NIHSS	9%	6%
Freedom from MRI Findings (Lesion Volume 0 mm³)	11%	27%
Lesion Volume (mm³)		
>0-50	7%	19%
>50-150	33%	7.5%
> 150	48%	46%

*15% Missing in MRI Follow-up and 5% missing for all other parameters
Type I Error = 5%*

Among subjects who reach third tier of the comparison hierarchy, we assume a 15% loss to DW-MRI follow-up (due to contraindications to post-procedure DW-MRI [e.g., pacemaker implantation] or subject non-compliance).

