12.1.1 Adaptive Design

Once at least 50% of the initial randomized Phase II cohort has been enrolled and has reached the 30 day primary efficacy endpoint evaluation time point, the independent unblinded statistician will perform a conditional power analysis. If the trial, based on the results at that point is either $\leq 40\%$ powered to achieve success in meeting the primary efficacy endpoint or is $\geq 80\%$ powered to achieve the primary efficacy endpoint no sample size reestimation will be required. If the conditional power of the study is $>40\%$ but $<80\%$ the independent unblinded statistician will recommend a sample size reestimation, subject to approval by the Sponsor. If this analysis determines that more than 225 randomized subjects

will be required to ensure adequate study power, enrollment may continue until the required number of subjects have been enrolled, or until the total subject limit for the study has been reached (whichever occurs first).

Promising zone computation

After the trial has enrolled 50% of the originally planned sample size of the initial randomized cohort (112 patients), an independent statistician will estimate all 4 levels of the Finkelstein-Schoenfeld hierarchy for device and control, and use these estimates to re-calculate the trial's power given the originally planned 225 Phase II patients.

If the trial power is between >40% and <80%, the trial will be considered promising and the trial will readjust the sample size to attain 80% power. If on the other hand the power falls to $\leq 40\%$ or $\geq 80\%$, the sample size will not be adjusted.

Conditional power computation

The conditional power will estimate all four Finkelstein-Schoenfeld levels and use these estimates to simulate future enrolled patients. The power simulation will follow exactly the same algorithm as used to power the original Phase II study with updated estimates of effect size.

Alpha spending and controlling type I error

Since the study leadership and sponsor do not conduct any formal statistical hypothesis test, this design will not incur any alpha penalty or affect the overall type I error. As detailed by Mehta and Pocock¹¹ and based on the work of Chen¹⁰ as long as the sample size reestimation occurs only when the conditional power falls in the promising zone, no additional alpha spend is required and the overall type I error is preserved.

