To determine the required sample size, calculations were performed by simulating 5000 samples on SAS software postulating the above parameters; mortality and stroke rates and proportions of patients with NIHSS worsening, any MRI lesions and volumes divided to subsets were simulated by a random binary function.

An evaluable sample size of 225 subjects (2:1 randomization with 150 in the Intervention group and 75 new Control subjects) is sufficient to demonstrate superiority of the Intervention group to the Control group for the primary efficacy endpoint when pair-wise comparisons are made between subjects using the Finkelstein-Schoenfeld method,² and outcomes between treatment groups are compared by the chi-square test.

Therefore, the initial randomized cohort sample size of 225 subjects (150 in the Intervention group and 75 new control subjects) will have >80% power to demonstrate superiority of the Intervention group for the primary efficacy endpoint (one sided $\alpha=0.025$). Notably, in several simulations, considering different distributions for lesion volume and different distributions for death/ stroke, the study power remained greater than 80%.

Adding the 63 control subjects already enrolled in REFLECT Phase I for a total of 138 control subjects would increase the power to at least 92% to demonstrate superiority of the primary efficacy endpoint. 5% loss to follow up is included.

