12.4.3 Primary Efficacy Endpoint

The primary hypothesis is that TAVI with the TriGuard HDH or TriGUARD 3 system is superior to standard (unprotected) TAVI for the primary hierarchical composite efficacy endpoint of all-cause mortality or any stroke at 30 days (Tier 1), followed by NIHSS worsening (increase from baseline) 2-5 days post-procedure (Tier 2), followed by any ischemic cerebral findings on DW-MRI (Tier 3), followed by total volume of post-procedure cerebral ischemic lesions detected by DW-MRI divided into preset subdivisions (Tier 4). Poolability of the Phase I and Phase II control subjects will be assessed at the time of the primary analysis and the results will determine the control population used for the primary analysis of the primary efficacy endpoint as detailed in the SAP.

The analytic approach is based on the statistical method described by Finkelstein and Schoenfeld.² A similar approach was used in PARTNER Trial (Cohort B) where the co-primary end point was hierarchical composite of the time to death from any cause or the time to the first occurrence of repeat hospitalization (after the index procedure) due to valve-related or procedure related clinical deterioration.¹⁰⁵ In addition, this approach was further explored and recommended for cardiovascular trials by Pocock et al.⁷⁷

In brief, we propose the following analysis methodology:

Each subject in the intervention group is compared with each and every subject from the control group based on the following prespecified hierarchy:

[figure not shown]
- All-cause mortality or any stroke (disabling or non-disabling) [evaluated at 30 days]
 - If both had a death/stroke a time to event analysis by days will determine a win
 - If both patients had a stroke at the same day the comparison moves to the next tier
- NIHSS worsening (increase from baseline) [evaluated at post-procedure (2 to 5 days post-procedure)]
- Freedom from any cerebral ischemic lesions detected by diffusion-weighted magnetic resonance imaging (DW-MRI) 2 to 5 days post-procedure
- Total volume of cerebral ischemic lesions detected by diffusion-weighted magnetic resonance imaging (DW-MRI) 2 to 5 days post-procedure

For example:

- If Subject A has stroke and Subject B survives free of stroke or death to 30 days, Subject B wins (score +1) and Subject A loses (score -1).
- If Subject A and Subject B both have death/stroke, time to event by day will determine a win.

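### The interim promising-zone rule is computed for 225 Phase II patients and is silent on the 63 Phase I controls, although the final primary test may include them

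*Combined protocol and SAP*

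**What the plan says.** Section 12.1.1 (repeated in the synopsis under Adaptive Design) has an independent statistician estimate the four tiers for device and control at about 112 subjects and recalculate power "given the originally planned 225 Phase II patients". The decision follows from that figure: "If the trial power is between >40% and <80%, the trial will be considered promising", and the sample size is then raised to reach 80% power. On method it says: "The power simulation will follow exactly the same algorithm as used to power the original Phase II study with updated estimates of effect size". The Phase I controls are not mentioned.

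The original powering, in section 12.2.4.1.2, gives two results. With 150 device subjects and 75 new controls the trial has ">80% power to demonstrate superiority of the Intervention group for the primary efficacy endpoint". Adding the 63 Phase I controls "for a total of 138 control subjects would increase the power to at least 92"%.

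The synopsis describes a primary comparison in which each Phase II device subject is "compared with every control subject (from phases I and II"). Section 12.4.3 makes this conditional: "Poolability of the Phase I and Phase II control subjects will be assessed at the time of the primary analysis", and the outcome decides which controls are used. Section 5.2 caps Phase II at 295 randomized subjects.

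**The concern.** A promising-zone rule works as intended only if the power it reads is the power of the test that will be run. Here the final test is either 150 against 75 or 150 against 138, and nobody knows which when the rule is applied. By the plan's own figures the two differ materially (above 80% against at least 92%).

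If the controls are later pooled, a rule read on the 225-patient scale can err in two directions. It can call for more patients when the pooled test already has 80% power, and it can refuse an increase when the pooled test is in the 40-80% zone. The first error could add up to 295 - 225 = 70 randomized subjects, about 47 of them to the device at 2:1. Section 5.1.1 justifies reusing Phase I controls partly by the wish to limit exposure to the device, so a rule that leaves them out works against that aim.

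**Working it through.** **1. Reproduce the plan's two power figures.** The signal of a two-group comparison scales with sqrt(nI × nC / (nI + nC)).

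- Phase II only: 150 × 75 / 225 = 50.
- Pooled: 150 × 138 / 288 = 71.875.
- Ratio: sqrt(71.875 / 50) = 1.199.

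At one-sided 0.025, pooled power = Φ(1.199 × (1.96 + z(p)) - 1.96), where p is the 225-patient power. For p = 80%, 1.96 + 0.842 = 2.802; 1.199 × 2.802 - 1.96 = 1.399; Φ(1.399) = 91.9%. This agrees with the stated 92%.

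A simulation of the Finkelstein-Schoenfeld test with the section 12.2.4.1.2 inputs, including the 30% reduction within volume classes, gave 80-94% for 225 subjects and 92-98% for 288. The closest scenario gave 80.2% and 92.2%. The spread comes from details the document does not give, such as the upper end of the largest volume class (assumed 500 to 3000 mm³).

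**2. Map the zone edges.**

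| Power on the 225-patient scale | Power of the pooled test (150 vs 138) |
|---|---|
| 29.6% | 40% |
| 40% | 53.4% |
| 64.7% | 80% |
| 80% | 91.9% |

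The pooled test's 40-80% zone is thus about 30-65% on the plan's scale, while the rule acts on 40-80%. The bands 65-80% and 30-40% are where the decision goes wrong if the controls are pooled.

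**3. How often the decisions differ.** Assumptions: unit-variance normal outcome; controls of both phases exchangeable and pooled at the end; at the interim 75 device, 37.5 Phase II control and 63 Phase I control subjects; true 225-patient power between 50% and 80%. Section 12.1.1 speaks both of recalculating the trial's power and of conditional power, so both were run.

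- *Power recalculated at the interim estimates, with the same estimates under both rules, so that only the final test differs:* disagreement in 18-20% of trials.
- *Conditional power.* With estimated difference δ and nC final controls, CP = Φ[(δ - 1.96 × sqrt(1/150 + 1/nC)) / sqrt(75/150² + 37.5/nC²)]. The 225-patient rule takes nC = 75 and Phase II controls only; the pooled rule takes nC = 138 and includes the 63 in δ. Disagreement is 25-30%: about 11-14% unneeded increases, 6.5-10% refused increases, and the rest disagreements in the other two directions. At true power of 80% the parts are 13.8 + 6.5 + 1.8 + 2.8 = 24.9%. There the 225-patient rule calls for an increase in 19.6% of trials, and in 13.8 / 19.6 = 70% of those the pooled conditional power is already at least 80%.

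**4. Type I error.** In 4 million null trials of the same normal model, with the 295 cap and the 40-80% zone, the rejection rate was 0.0246 for a 225-patient rule followed by a pooled final test. It was also 0.0246 when rule and test were both Phase II only.

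**The case against.** **The text does not exclude the Phase I controls.** Naming 225 Phase II patients may only fix Phase II enrolment at its unincreased size, and the original powering to which section 12.1.1 refers was reported both ways. This stands as a caveat: Phase II only is the natural reading but an inference. A reader might infer that the plan expressly bars the Phase I controls from the interim; it does not. If pooling was intended, the rule is unspecified and needs the same correction. Sections 5.1.1 and 12.4.3 also refer poolability details to the SAP; no separate SAP text on this is in the document supplied.

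**Using Phase II controls is prudent.** Only they are certain to be in the final test. The Phase I controls came from US, European and Israeli sites under partly different exclusions, whereas Phase II is US only. An increase is unneeded only if pooling later goes ahead. This is fair, but section 12.1.1 does not give it as the reason, and in the 30-40% band the choice blocks an increase, which is not conservative.

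**The size is easily overstated.** A reader might infer that about a third of trials are affected. A figure of 32-36% arises only if power is re-estimated unconditionally and the Phase I controls also enter the interim estimates, which mixes two changes. Nor would every unneeded increase reach 70: on the same scaling, 75% power needs 225 × (2.802 / 2.634)² ≈ 255 subjects, about 30 extra, and 79% needs about 6 extra. The increase also requires sponsor approval.

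**No harm to validity.** A reader might infer that the mismatch undermines the type I error statement in section 12.1.1. The check above found no inflation, under a normal model with exchangeable controls.

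**Conclusion.** The point holds as a mismatch between the interim decision rule and the final test. Followed as written, the plan can size Phase II for 150 against 75 and then test 150 against 138. If the controls are pooled, the zone is misplaced by roughly 10 to 15 percentage points at its edges (30-65% against 40-80%). Decisions then differ in about 18-20% of trials when only the final test changes, and in 25-30% under conditional power. These rates assume exchangeable controls that do get pooled and true 225-patient power of 50-80%; if pooling fails, the Phase II rule matches the test that is run. What is at stake is efficiency and patient exposure, or an increase forgone, not the validity of the final test. It should be corrected before the interim.

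**What to change.** Amend section 12.1.1 and the matching synopsis text to say which controls enter the interim estimates, and to compute conditional power for the test that will be primary.

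Preferred: fix the control set before the interim power is computed, by a poolability assessment that compares Phase I with Phase II controls only and is blind to device-arm outcomes. Change the timing in section 12.4.3 and the synopsis to match. The price is that only about 37 Phase II controls are then available instead of 75. For illustration, with an assumed test level of 0.15 (two-sided) and an assumed shift of 0.4 SD between phases, detection is Φ(0.4 / sqrt(1/63 + 1/75) - 1.44) = 82% with 75 and Φ(0.4 / sqrt(1/63 + 1/37) - 1.44) = 69% with 37.

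Otherwise: compute conditional power for both control sets at the interim and pre-specify which one governs the decision. This needs only extra analysis and wording. Making Phase II controls alone the primary set would also align rule and test, but it gives up the 92% power the plan expects from pooling.

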12.2 Sample Size Calculation

12.2.1 Hypotheses

12.2.1.1.1 Primary Safety Hypothesis (Phase I and Phase II reported individually)

The primary safety hypothesis is that the rate of the primary safety endpoint (a composite of death, stroke, life-threatening or disabling bleeding, AKI [Stage 2 OR 3], coronary artery obstruction requiring intervention, major vascular complication, and valve-related dysfunction requiring repeat procedure) in the group undergoing TAVI with either protection device system (Intervention Groups) at 30 days will be less in each device group (TriGuard HDH and TriGUARD 3) compared separately to a performance goal (PG) of 34.4%.

Specifically, the primary safety analysis will assess if the Intervention group's safety event rate is significantly less than the PG of 34.4% using a one-sample z-test of proportions. The formal null and alternative hypotheses to be tested are:

$$H_0: \pi \geq 0.344$$

$$H_1: \pi < 0.344$$

where π is the true safety event rate for the Intervention arm.

The primary hypothesis test will be carried out by comparing the upper bound of the one-sided 95% confidence interval of the primary safety endpoint event rate in the intervention arm to the PG. With the planned evaluable sample size of 179 subjects and a one-sided alpha of 0.05, the critical value for rejection of the null hypothesis is 28.5%: if the primary

safety endpoint occurs in 28.5% or less of intervention group subjects, the performance goal will be met.

After accounting for a potential 5% loss to clinical follow-up at 30 days (including subjects who do not meet As Treated population criteria), the total required intervention group sample size is 190 subjects in each Phase. For Phase II 150 subjects randomized to the TriGUARD 3 and the 40-50 roll-ins will constitute the primary safety population.

Trial success depends on both primary endpoints being met in their primary analysis populations; i.e., the primary safety endpoint must be met in the primary (AT) population and the primary efficacy endpoint must be met in the primary (eITT) population in order for the trial to be declared a success. Because both primary endpoints (safety and efficacy) must be met (i.e., both H_0 must be rejected) for the trial to be declared a success, no adjustment to alpha for multiple endpoints is required for the two primary study endpoints.

12.2.1.1.2 Primary Efficacy Hypothesis

The primary hypothesis is that TAVI with the TriGUARD 3 system is superior to standard (unprotected) TAVI for the primary hierarchical composite efficacy endpoint of all-cause mortality or any stroke at 30 days (Tier 1), NIHSS worsening from baseline assessed at 2-5 days post-procedure (Tier 2), freedom from any cerebral ischemic lesions detected by diffusion-weighted magnetic resonance imaging (DW-MRI) 2 to 5 days post-procedure (Tier 3), and total volume of post-procedure cerebral ischemic lesions detected by DW-MRI (Tier 4).

Specifically, the primary efficacy hypotheses are:

H_0 : The hierarchical composite of death/stroke, NIHSS worsening, freedom from any lesions detected by DW-MRI, and larger total lesion volumes is not different between Intervention and Control groups

H_1 : The hierarchical composite of death/stroke, NIHSS worsening, freedom from any lesions detected by DW-MRI, and larger total lesion volumes is lower in the Intervention group than in the Control group

The null hypothesis will be tested at the final analysis at a one-sided 0.025 level of significance. The null hypothesis will be tested using the chi-square test according to the method described in Finkelstein-Schoenfeld² and Pocock⁷⁷.

12.2.1.1.3 Hypothesis-driven Secondary Endpoints

In order to control alpha at 0.025 level overall, the secondary endpoints will be tested if and only if the primary study endpoints are met. Secondary testing will be conducted sequentially beginning with all stroke, followed by NIHSS worsening, followed by the composite of all-cause mortality and all stroke, followed by CNS Infarction, followed by total volume of cerebral ischemic lesions.

- **All stroke** [evaluated at 7 days in the eITT analysis population]

The hypothesis is that the event rate for all stroke in the Intervention Group at 7 days will be lower than the Control Group at 7 days.

The formal null and alternative hypotheses to be tested are:

$$H_0: \pi_{STRK-I} = \pi_{STRK-C}$$

$$H_1: \pi_{STRK-I} < \pi_{STRK-C}$$

where π_{STRK-I} is the true rate of all stroke in the Intervention arm and π_{STRK-C} is the true rate of all stroke in the Control arm.

The null hypothesis will be tested at a one-sided 0.025 level of significance using a two-sample z-test of proportions.

- **NIHSS worsening**, defined as an NIHSS score increase from baseline [evaluated at 2-5 days post-procedure in the efficacy Intention to Treat (eITT) analysis population]

The hypothesis is that the rate of the patients with worsening NIHSS score in the Intervention Group at post-procedure (2-5 days post-procedure) will be lower than the Control Group at post-procedure (2-5 days post-procedure).

The formal null and alternative hypotheses to be tested are:

$$H_0: \pi_{NIHSS-I} = \pi_{NIHSS-C}$$

$$H_1: \pi_{NIHSS-I} < \pi_{NIHSS-C}$$

where $\pi_{NIHSS-I}$ is the true rate of worsening NIHSS scores in the Intervention arm and $\pi_{NIHSS-C}$ is the true rate of worsening NIHSS scores in the Control arm.

The null hypothesis will be tested at a one-sided 0.025 level of significance using a two-sample z-test of proportions.

- **Composite of all-cause mortality and all stroke** [evaluated at 7 days in the eITT analysis population]

The hypothesis is that the event rate for the composite of all-cause mortality and all stroke in the Intervention Group at 7 days will be lower than the Control Group at 7 days.

The formal null and alternative hypotheses to be tested are:

$$H_0: \pi_{COMP-I} = \pi_{COMP-C}$$

$$H_1: \pi_{COMP-I} < \pi_{COMP-C}$$

where π_{COMP-I} is the true rate of the composite of all-cause death and all stroke in the Intervention arm and π_{COMP-C} is the true rate of the composite of all-cause death and all stroke in the Control arm.

The null hypothesis will be tested at a one-sided 0.025 level of significance using a two-sample z-test of proportions.

- **CNS infarction** (NeuroARC defined) [evaluated at 30 days in the eITT analysis population]

The hypothesis is that the event rate for CNS infarction in the Intervention Group at 30 days will be lower than the Control Group at 30 days.

The formal null and alternative hypotheses to be tested are:

$$H_0: \pi_{CNS-I} = \pi_{CNS-C}$$

$$H_1: \pi_{CNS-I} < \pi_{CNS-C}$$

where π_{CNS-I} is the true rate of CNS infarction in the Intervention arm and π_{CNS-C} is the true rate of CNS infarction in the Control arm.

The null hypothesis will be tested at a one-sided 0.025 level of significance using a two-sample z-test of proportions.

- **Total volume of cerebral ischemic lesions** detected by DW-MRI, [evaluated 2 to 5 days post-procedure in the efficacy Intention to Treat (eITT) analysis population]

The hypothesis is that the total volume of cerebral ischemic lesions in the Intervention Group will be lower than the Control Group.

The formal null and alternative hypotheses to be tested are:

$$H_0: \pi_{TLV-I} = \pi_{TLV-C}$$

$$H_1: \pi_{TLV-I} < \pi_{TLV-C}$$

where π_{TLV-I} is the true total volume of cerebral ischemic lesions in the Intervention arm and π_{TLV-C} is the true total volume of cerebral ischemic lesions in the Control arm.

The null hypothesis will be tested at a one-sided 0.025 level of significance using the two-sample z-test.

